9.4. Demographics and Baseline Characteristics

Demographic and clinical characteristics of subjects enrolled onto this study will be summarized. For categorical variables, frequencies and percentages will be provided. Means with standard deviations or medians/percentiles will summarize non-categorical variables.

9.5. Treatment

A frequency distribution will be generated for the dose levels administered. Any deviations to the dose-escalation criteria will also be noted.

9.6. Efficacy

9.6.1. Efficacy Endpoints

9.6.1.1. Primary Efficacy Endpoint

- The proportion of subjects with either a normal 24-hr UFC or a reduction in 24-hr UFC of $\geq 50\%$ relative to their baseline value at the end of the double-blind randomized withdrawal period

9.6.1.2. Secondary Efficacy Endpoints

The secondary efficacy endpoints will include the following. If the data allow, unless otherwise specified in the Statistical Analysis Plan, the endpoints will be evaluated for each post-baseline

visit, at the end of the open-label dose-escalation period and at the end of the double-blind randomized withdrawal period, for the ITT population as a whole and for each baseline UFC stratum.

- The proportion of subjects with a normal 24-hr UFC at the end of the double-blind randomized withdrawal period
- The proportion of subjects with a reduction in 24-hr UFC of $\geq 50\%$ relative to their baseline value at the end of the double-blind randomized withdrawal period
- The proportion of subjects with a normal 24-hr UFC at the end of the open-label dose-escalation period and at the end of the additional open-label dosing period
- The proportion of subjects with a reduction in 24-hr UFC of $\geq 50\%$ relative to their baseline value at the end of the open-label dose-escalation period and at the end of the additional open-label dosing period
- The change and percentage change in the 24-hr UFC from randomization at the end of the double-blind randomized withdrawal period
- The change and percentage change in the 24-hr UFC from baseline at the end of the open-label dose-escalation period and at the end of the additional open-label dosing period
- The proportion of subjects with a normal late night salivary cortisol at the end of the double-blind randomized withdrawal period
- The proportion of subjects with a normal late night salivary cortisol at the end of the open-label dose-escalation period and at the end of the additional open-label dosing period
- The change and percentage change in the late night salivary cortisol from randomization at the end of the double-blind randomized withdrawal period
- The change and percentage change in the late night salivary cortisol from baseline at the end of the open-label dose-escalation period and at the end of the additional open-label dosing period
- The change and percentage change from baseline in blood hormone levels, including 11-DOC, 17-OHP, A, A4, ACTH, cortisol, DHEA, DHEAS, free T, P, renin, SHBG and total T
- The change from baseline in fasting glucose, insulin, lipid panel, systolic blood pressure, diastolic blood pressure and BMI

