3.1.2. Open-Label Dose-Escalation Period

The open-label dose-escalation period will be 8 weeks in duration and will allow each subject to receive three dose levels of ATR-101 (i.e., **250 mg BID**, **500 mg BID**, and **1000 mg BID**). The 250 mg and 500 mg BID dose levels will each be used for 2 weeks, and the 1000 mg BID dose level will be used for 4 weeks.

- **Study Days 1-14:** At Visit T1, all subjects will be assigned to take the same starting dose of ATR-101, 250 mg BID, at the beginning of the open-label dose-escalation period. Twenty-four-hour UFCs will be assessed on Days 13 and 14 (collections start on Days 13 and 14, respectively, and finish on Days 14 and 15, respectively).
- **Study Days 15-28:** At Visit T2, all subjects will be assigned to take the next higher dose of ATR-101, 500 mg BID. Twenty-four-hour UFCs will be assessed on Days 27 and 28

(collections start on Days 27 and 28, respectively, and finish on Days 28 and 29, respectively).

- **Study Days 29-56:** At Visit T3, all subjects will be assigned to take the next higher dose of ATR-101, 1000 mg BID. Twenty-four-hour UFCs will be assessed on Days 41, 42, 50, 51, and 56 (collections start on Days 41, 42, 50, 51, and 56, respectively, and finish on Days 42, 43, 51, 52, and 57, respectively).

At any time, the ATR-101 dose may be down-titrated as needed for safety reasons at the discretion of the Investigator. There will be no wash-out period between the open-label dose-escalation period and either the double-blind randomized withdrawal period or the additional open-label dosing period.

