3.1.3. Double-blind Randomized Withdrawal Period

The double-blind randomized withdrawal period will be up to 4 weeks in duration. A subject is eligible to enter the double-blind randomized withdrawal period if the mean of the Day 50 and Day 51 (“mean Day 50/51”) 24-hr UFCs meets at least one of the following randomization criteria:

- 24-hr UFC \leq ULN
- 24-hr UFC \leq 50% relative to the baseline value

Eligible subjects will be randomized in a 1:1 ratio to receive either ATR-101 at the same dose level being used at the completion of the open-label dose-escalation period (expected to be 1000 mg BID) or matching placebo. Subjects will continue in the double-blind randomized withdrawal period for 4 weeks or until their mean Day 64/65 24-hr UFC is $> 1.3 \times$ ULN and has also increased by $> 50\%$ relative to their mean Day 50/51 24-hr UFC, whichever comes first. Subjects who are not eligible to be randomized will enter the Additional Open-Label Dosing Period instead of the Double Blind Randomized Withdrawal Period (see below).

- **Study Days 57-70:** Twenty-four-hour UFCs will be collected on Days 64 and 65 (collections start on Days 64 and 65, respectively, and finish on Days 65 and 66, respectively). At the time of Visit R2 (Day 71), if the mean Day 64/65 24-hr UFC result is available and is $> 1.3 \times$ ULN, and has also increased by $> 50\%$ relative to the mean Day 50/51 24-hr UFC, the subject will complete the End-of-Treatment (EoT) visit (Visit R3) instead of Visit R2 and may then be started on another agent at the discretion of his or her physician. Otherwise, the subject will continue in the double-blind, randomized withdrawal period.
- **Study Days 71-85:** Twenty-four-hour UFCs will be collected on Days 79 and 84 (collections start on Days 79 and 84, respectively, and finish on Days 80 and 85, respectively). The EoT visit (Visit R3) will be completed on Day 85. Note: if the mean Day 64/65 24-hr UFC was not available at the time of Visit R2, but subsequently is found to meet criteria for study completion, the EoT visit should be performed as soon as practicable, rather than on Day 85. Additionally, if the Day 79 or Day 84 24-hr UFC is $>$ ULN, after completion of the EoT visit (Visit R3) the subject may begin treatment with another agent at the discretion of his or her physician.

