3.5. Treatment Assignment

There are a total of 3 dose levels for ATR-101 during the open-label dose-escalation period:

- 250 mg BID
- 500 mg BID
- 1000 mg BID

All enrolled subjects will be assigned to take the same starting dose of ATR-101, 250 mg BID. Dose escalation to the next higher dose of ATR-101, 500 mg BID, will occur at Visit T2. Further dose escalation to the next higher dose of ATR-101, 1000 mg BID, will occur at Visit T3.

A subject may enter the double-blind randomized withdrawal period if the mean Day 50/51 24-hr UFC is \leq ULN or \leq 50% relative to the baseline value. Such subjects will be randomized 1:1 to receive either ATR-101 at the same dose level on which they achieved the mean Day 50/51 24-hr UFC \leq ULN (or \leq 50% of their baseline value) (expected to be 1000 mg BID) or matching placebo in a double-blinded manner.

Subjects who do not meet any of the randomization criteria will enter the additional open-label dosing period and receive ATR-101 1000 mg BID.

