9.3. Analysis Populations

Efficacy – The primary efficacy analysis population will be the Intent-to-Treat (ITT) population, based on all subjects who are randomized to the double-blind randomized withdrawal period and take at least one dose of double-blind study drug. The modified ITT (mITT) population, based on all subjects who complete at least 2 weeks in the double-blind randomized withdrawal period of the study, will be used for additional analyses. For efficacy analyses, subjects will be included in the treatment group to which they were randomized.

Safety – The safety population will include all treated subjects. Safety analyses will be based on the safety population. For the safety analyses for the double-blind randomized withdrawal period, subjects randomized to the placebo group who receive ATR-101 will be included in the treatment group of the active study drug that they received.

Pharmacokinetic – The PK population will include all subjects with measurable drug concentrations. PK analyses will be based on the PK population.

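### The default population for the secondary endpoints is ITT, so open-label dose-escalation UFC results are reported only in subjects selected for having responded

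*Protocol*

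**What the plan says.** - **Population for the secondary endpoints.** Section 9.6.1.2 opens "If the data allow, unless otherwise specified in the Statistical Analysis Plan, the endpoints will be evaluated for each post-baseline" visit, then adds the end of dose escalation and the end of the withdrawal period, "for the ITT population as a whole and for each baseline UFC stratum". The synopsis sets the same default, also subject to the SAP.
- **Endpoints listed under that sentence.** Of 12 bullets, five concern results "at the end of the open-label dose-escalation period and at the end of the additional open-label dosing period": normal UFC, UFC reduction of at least 50%, change in UFC, normal late night salivary cortisol, and change in late night salivary cortisol.
- **ITT.** Section 9.3 defines it as "based on all subjects who are randomized to the double-blind randomized withdrawal period and take at least one dose of double-blind study drug".
- **mITT.** The only other efficacy population is "based on all subjects who complete at least 2 weeks in the double-blind randomized withdrawal period of the study". The all-treated set in section 9.3 is assigned to safety analyses only.
- **Who is randomised.** Section 3.1.3: "A subject is eligible to enter the double-blind randomized withdrawal period if the mean of the Day 50 and Day 51" UFCs is at or below ULN, or is at most 50% of baseline.
- **Who is not.** Section 3.5: "Subjects who do not meet any of the randomization criteria will enter the additional open-label dosing period".
- **UFC collections on the top dose.** Section 3.1.2: "Twenty-four-hour UFCs will be assessed on Days 41, 42, 50, 51, and 56".

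**The concern.** Entry to ITT depends on the outcome that the dose-escalation endpoints measure. A rate of UFC response at the end of dose escalation, computed in ITT, is a rate among subjects already chosen for a UFC response about a week earlier. It does not describe how often the drug works in the subjects who took it.

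This matters because dose escalation is the only period to which all of the roughly 16 enrolled subjects contribute, and section 1.4 describes the study as proof of concept. Under the default, normal UFC, reduction of at least 50% and change from baseline would all look better than in the treated group.

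The additional open-label period has the opposite problem. Section 3.2 says it exists to assess efficacy after longer dosing, yet its subjects belong to no efficacy population in section 9.3.

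**Working it through.** The protocol states that no formal sample size calculation was performed, so there is no planned figure to reproduce. The check has two parts: logic that needs no assumption, and a simulation that shows the possible size.

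**1. Set logic (sections 3.1.3, 3.5, 9.3, 9.6.1.2)**

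Let B be baseline UFC and G the mean Day 50/51 UFC, both in multiples of ULN. The randomisation criterion is G ≤ 1 or G ≤ 0.5 × B.

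- Every ITT subject meets the composite response on G by construction. If k of 16 enrolled subjects pass and are dosed, the composite rate is k/k = 100% in ITT and k/16 in all enrolled:

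| k | ITT | All enrolled | Not in ITT |
|---|---|---|---|
| 2 | 100% | 12.5% | 14 |
| 4 | 100% | 25% | 12 |
| 8 | 100% | 50% | 8 |
| 12 | 100% | 75% | 4 |

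- If B ≥ 2, then G ≤ 1 implies G ≤ 0.5 × B. Passing therefore forces a reduction of at least 50%. This covers all of Stratum II (4 to 10 × ULN).
- If B ≤ 2, then G ≤ 0.5 × B implies G ≤ 1. Passing therefore forces a normal value.
- After Day 57 a subject enters either the withdrawal period or the additional open-label period. ITT therefore contains 0 subjects from the latter. The lead sentence of 9.6.1.2 does not name the end of that period, so the five endpoints there have either n = 0 (if ITT is applied) or no stated population.

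**2. Size of the bias**

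Assumptions, none of them from the protocol:

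- true UFC log-uniform over 0.8-14 × ULN;
- log-normal on-drug ratio to baseline, with median 0.70 (SD of log 0.4) or 0.55 (SD of log 0.5);
- within-subject CV 20%, 30% or 50%, with independent collections;
- everyone who passes is randomised and dosed.

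Protocol rules applied: mean of two screening UFCs 1.3-10 × ULN with neither normal; the Day 50/51 criterion as above; Day 56 as one further collection. The ranges are over the three CVs.

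| | Median 0.70: all treated | ITT | Median 0.55: all treated | ITT |
|---|---|---|---|---|
| Share passing | 26-32% | | 46-47% | |
| Day 56, reduction ≥50% | 24-35% | 63-68% | 44-48% | 73-81% |
| Day 56, normal UFC | 12-16% | 32-36% | 21-24% | 40-42% |
| Day 56, median change | -31 to -34% | -57 to -59% | -45 to -48% | -63 to -66% |
| Day 50/51 mean, reduction ≥50% | 23-30% | 87-94% | 43-45% | 93-96% |
| Day 50/51 mean, normal UFC | 11-13% | 40-43% | 21% | 45% |

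With a stronger drug (median 0.40, SD of log 0.3), the Day 56 rate of a reduction of at least 50% is 66-73% in all treated and 78-86% in ITT. The gap is 78 - 66 = 12 to 86 - 73 = 13 points. Normal UFC is 33-34% against 41-43%.

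A simpler model uses only the criterion of at most half of baseline, with between-subject SD 0.5 and within-subject SD 0.2-0.5 on the log scale. For a reduction of at least 50% at Day 56, all enrolled against ITT, it gives 15-25% against 62-75% (median 0.9), 28-36% against 69-80% (median 0.7) and 51-53% against 76-86% (median 0.5).

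ITT is the more favourable in every setting. The gap narrows as more subjects respond, because fewer are then excluded.

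**The case against.** **The population is left to the SAP.** The sentence yields to the SAP and applies only if the data allow, and the SAP is not shown. This limits what can be said about the eventual report. It does not repair the protocol, which states a default that misleads if followed. Data at the end of dose escalation will normally exist for ITT subjects, so the feasibility clause would not stop the analysis.

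**The n = 0 reading is artificial.** The lead sentence does not name the end of the additional open-label period, and nobody would run an empty table; the natural denominator is those who entered. This largely stands. What remains is an unstated denominator, which causes no bias and is close to SAP detail.

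**Day 56 is the natural end of dose escalation.** It is the last collection in the period, and Day 50/51 has its own purpose. This is reasonable, and it makes the Day 56 rows the ones to weigh. The text still does not say so, and the bias in the rate of reduction of at least 50% is larger on the Day 50/51 mean.

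**The size is not known.** This is correct. It depends on a response rate and variability that the protocol does not give. Only the direction is robust.

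**The criterion uses UFC only.** The calculations do not cover salivary cortisol, blood hormones, metabolic measures, blood pressure or BMI. Those endpoints share the wrong denominator, but no size is claimed for them.

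**An ITT table has a use.** It describes the randomised subjects as they enter withdrawal. It can be kept for that purpose, but not as the stated analysis of dose-escalation efficacy.

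**Conclusion.** The concern holds and should be fixed. Sections 3.1.3, 9.3 and 9.6.1.2 read together make the default dose-escalation UFC results conditional on response, and section 9.3 offers no efficacy population that contains the non-randomised subjects. These statements rest on the definitions alone.

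The upward direction for the UFC endpoints held in every setting examined. For a reduction of at least 50% at Day 56, the main model gives gaps from about 12 points (median on-drug UFC 40% of baseline) to about 44 points (68% against 24%, median 70%). These sizes are illustrations under assumed response and variability, not predictions. The primary endpoint and the randomised comparison are not affected. A SAP that names other populations would remove the problem in practice.

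**What to change.** In section 9.6.1.2 and the matching synopsis text:

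1. Limit ITT to the endpoints of the double-blind withdrawal period.
2. Analyse the dose-escalation endpoints in all treated subjects, which is the existing safety population, overall and by baseline UFC stratum. An ITT summary at entry to withdrawal may be added if labelled as descriptive of the randomised subjects.
3. Analyse the additional open-label endpoints in all subjects who enter that period.
4. State whether the Day 50/51 mean or the Day 56 UFC defines the end of dose escalation.

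Handling of missing UFC values can stay with the SAP. The cost is wording only, with no new data. Reported open-label response rates will be less favourable, and the open-label and double-blind tables will have different denominators, which the table titles should state.

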4. SELECTION AND WITHDRAWAL OF SUBJECTS

4.1. Inclusion Criteria

Each subject must meet all of the following criteria to be enrolled in this study:

1. Provision of signed and dated informed consent prior to any study-specific procedures
2. Men and women 18-80 years of age (inclusive) at screening
3. Subjects must have a confirmed diagnosis of endogenous Cushing's syndrome as evidenced by baseline UFC 1.3 to 10 \times ULN (mean of all 24-hr UFC levels obtained during the screening period within 28 days of enrollment into the open-label dose-escalation period) AND documentation at any time of ONE of the following three criteria:
 - For subjects with a diagnosis of pituitary Cushing's syndrome, either:
 - Magnetic resonance imaging (MRI) confirmation of pituitary adenoma (greater than or equal to 0.6 cm), OR
 - For subjects with a pituitary microadenoma less than 0.6 cm, bilateral inferior petrosal sinus sampling (BIPSS) showing an ACTH gradient > 2 before or > 3 after corticotropin-releasing hormone (CRH) or desmopressin (DDAVP) stimulation, OR
 - For subjects who have had prior pituitary surgery: histopathology confirming an ACTH-staining adenoma
 - For subjects with a diagnosis of adrenal Cushing's syndrome: MRI or computed tomography (CT) of the adrenal glands showing an adrenal tumor
 - For subjects with a diagnosis of ectopic ACTH as the cause of their Cushing's syndrome: ACTH-dependent Cushing's syndrome and either:
 - MRI showing no pituitary adenoma, OR
 - MRI showing only a small pituitary adenoma (< 0.6 cm) AND a negative BIPSS, OR
 - For subjects who have had prior pituitary surgery: histopathology that is negative for an ACTH-staining adenoma
4. Subjects with a history of prior pituitary surgery must be at least 3 months post-surgery at the time of the screening visit
5. Body mass index (BMI) between 18 and 60 kg/m², inclusive, at screening

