4.2. Exclusion Criteria

Subjects who meet any of the following criteria will be excluded from participation in the study:

1. Pseudo-Cushing's syndrome, cyclic Cushing's syndrome or current iatrogenic Cushing's syndrome

2. Subjects who are considered candidates for surgical treatment of Cushing's syndrome, unless it is clearly documented that the subject has refused such surgery or that surgery cannot be scheduled for at least the anticipated duration of the study
3. Normal late night salivary cortisol value during screening unless the subject's history clearly demonstrates that he or she does not have pseudo-Cushing's or cyclic Cushing's. If the subject has a normal late night salivary cortisol, and the PI feels the subject does not have pseudo-Cushing's or cyclic Cushing's, the subject may be enrolled with approval of the medical monitor
4. Normal 24-hr UFC during screening (this would be suggestive of cyclic Cushing's)
5. Radiotherapy of the pituitary within 6 months prior to or during screening
6. For subjects with pituitary Cushing's syndrome, any compression of the optic chiasm or the presence of a tumor within 2 mm of the optic chiasm on the most recent pituitary MRI prior to or during screening
7. Use of or medical requirement for any of the following medications within the timeframes specified below prior to collection of the first 24-hr UFC during Screening and throughout study participation (see Section 5.11 for additional prohibited and restricted medications):
 - Inhibitors of steroidogenesis (ketoconazole, metyrapone): 1 week
 - Pituitary-directed agents: Dopamine agonists (bromocriptine, cabergoline) and PPAR γ agonists (rosiglitazone or pioglitazone): 4 weeks
 - Octreotide LAR, Lanreotide SR and Lanreotide autogel: 14 weeks
 - Octreotide (immediate release formulation): 1 week
 - Pasireotide: 4 weeks
 - Mitotane: 26 weeks
 - Mifepristone: 3 weeks
8. Uncontrolled diabetes mellitus, as evidenced by HbA1c > 9.0% at screening
9. Uncontrolled hypertension, defined as systolic blood pressure > 160 mmHg or diastolic blood pressure > 90 mmHg during screening. Note: if appropriate, subjects may have blood pressure medications adjusted and blood pressure reassessed at an unscheduled visit prior to Visit T1.
10. Any history of gastric or small intestinal surgery or any current disease that causes malabsorption. Note: irritable bowel syndrome is acceptable for inclusion

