6.10.1. Efficacy Assessments

6.10.1.1. 24-Hour Urinary Free Cortisol

24-hr urine collections for assessment of UFC will be performed using the standard procedure (see Laboratory Manual). If a urine collection is suspected to be incomplete, a repeat 24-hr UFC may be performed with approval of the Medical Monitor.

Two collections will be done during the screening period, within 28 days prior to enrollment into the open-label dose-escalation period (Visit T1), and results reviewed for eligibility prior to enrollment. Subjects who require wash-out of medications should perform these collections AFTER wash-out.

During the Open-Label Dose-Escalation Period of the study, subjects will begin a 24-hr urine collection on Days 13, 14, 27, 28, 41, 42, 50, 51, and 56. In addition, subjects in the Double-Blind Randomized Withdrawal Period of the study will begin a 24-hr urine collection on Days 64, 65, 79, and 84; and subjects in the Additional Open-Label Dosing Period of the study will begin a 24-hr urine collection on Days 69, 70, 79, and 84. The collections that occur within 2 days before study visits should be brought to the corresponding study visit (along with any other samples that had not been previously submitted). For all other collections, when completed, a visiting nurse may assist with processing and shipping these 24-hr collections to the central laboratory, or the subject may submit them to the study site, per subject preference.

The mean of the Day 50 and the Day 51 (“mean Day 50/51”) 24-hr UFC results will be used by the Investigator to determine whether the subject meets criteria for randomization. For subjects in the Double-Blind Randomized Withdrawal Period of the study, the mean of the Day 64 and the Day 65 (“mean Day 64/65”) 24-hr UFC results, if available at the time of Visit R2, will be used by the Investigator to determine whether the subject should undergo Visit R3 rather than Visit R2. The Day 79 result and the Day 84 result will be used to make the initial determinations of whether the subject’s follow-up visit should be conducted at the study site or via telephone.

In addition, subjects whose Day 84 24-hr UFC is \leq ULN will collect an additional 24-hr urine sample for UFC on Day 92. This result, if available at the time the Day 98 visit is due, will also be used to determine whether the subject’s follow-up visit should be conducted at the study site or via telephone.

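### Open-label UFC response rates default to the randomized-only ITT population and need no averaged or confirmed value, so they describe a pre-selected group and can include chance responders

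*Protocol*

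**What the plan says.** Entry requires endogenous Cushing's syndrome "as evidenced by baseline UFC 1.3 to 10" × ULN, taken as the mean of the screening values (Section 4.1). A normal UFC during screening excludes the subject (Section 4.2, criterion 4). On the number of samples, Section 6.10.1.1 says: "Two collections will be done during the screening period, within 28 days prior to enrollment into the open-label dose-escalation period".

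Section 9.6.1.2 then lists "The proportion of subjects with a normal 24-hr UFC at the end of the open-label dose-escalation period", with a counterpart for the additional open-label period. A separate endpoint counts falls of 50% or more, judged "relative to their baseline value at the end of the open-label dose-escalation period and at the end of the additional open-label dosing period". Neither asks for an average, a repeat or a minimum fall. The same section says that the secondary endpoints are evaluated in the ITT population and by baseline UFC stratum, if the data allow and unless the SAP specifies otherwise.

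At the last dose level, "Twenty-four-hour UFCs will be assessed on Days 41, 42, 50, 51, and 56" (Section 3.1.2). The protocol gives the averaged Day 50/51 pair a different job: the mean of those "24-hr UFC results will be used by the Investigator to determine whether the subject meets criteria for randomization" (Section 6.10.1.1). Baseline and the Day 64/65 study-completion check are also averages.

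**The concern.** There are two separate weaknesses.

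**Population.** ITT is formed at Day 57 from subjects whose mean Day 50/51 UFC has just met a response criterion. A response rate at the end of dose escalation taken in that group largely repeats the gate. It leaves out the subjects who did not respond, which is the information an open-label rate should carry. Subjects in the additional open-label period are never randomized, so none of them belongs to ITT.

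**Measurement.** Near the entry floor, a modest change in one urine turns an eligible subject into a normal one, and no control arm shows how often that happens without a drug effect.

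The trial is meant to establish proof of concept (Section 1.4) with about 16 subjects, of whom only some will be randomized. If few are, the open-label proportions will carry much of the efficacy description, and one or two chance responders would be visible in them.

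**Working it through.** The protocol gives no response rate, no UFC variability and no sample-size calculation, so there is no figure of its own to reproduce.

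**1. Populations side by side**
- ITT (Section 9.3): randomized, and at least one dose of double-blind drug.
- Randomized (Section 3.1.3): mean Day 50/51 UFC ≤ ULN or ≤ 50% of baseline.
- Additional open-label period (Section 3.1.4): subjects who meet neither criterion, hence never randomized.

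ITT and the additional open-label group do not overlap, so that period's endpoint has n = 0 in ITT.

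For dose escalation, let r of 16 be randomized, with x responders among them and y among the other 16 − r. ITT reports x/r. All enrolled gives (x + y)/16. The first is larger whenever x/r > y/(16 − r), which the gate makes likely because Day 56 is only 56 − 51 = 5 days after the values that formed it.

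A no-effect simulation shows the pull of the gate. With CV 30-50%, and true UFC lognormal with median 1.5, 2 or 3 × ULN and log-SD 0.6-0.7, the Day 56 normal rate is 1.5-11% in all enrolled and 10-26% in ITT.

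**2. Fall needed to become normal: 1 − 1/B for baseline B × ULN**
- B = 1.3: 23%
- B = 2: 50%
- B = 4: 75%
- B = 10: 90%

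**3. Chance that one value is ≤ ULN with no drug effect**

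For a true median M × ULN, P = Φ(−ln M / σ), with σ = √ln(1 + CV²). Example for M = 1.3 and CV 30%: σ = 0.294, ln 1.3 = 0.262, P = Φ(−0.89) = 19%.

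| True median (× ULN) | CV 30% | CV 40% | CV 50% |
|---|---|---|---|
| 1.3 | 19% | 25% | 29% |
| 1.5 | 8% | 15% | 20% |
| 2 | 1% | 4% | 7% |
| 4 | about 0 | about 0 | 0.2% |

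**4. The whole screening rule, no drug effect, single Day 56 value**

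Assumptions: true UFC lognormal, median 1.5, 2.5 or 4 × ULN, log-SD 0.6; two screening values, both > ULN, with mean 1.3-10. Ranges run over the medians.

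| All enrolled | CV 30% | CV 40% | CV 50% |
|---|---|---|---|
| Normal | 0.7-5% | 1.5-9% | 3-13% |
| Expected in 16 (16 × rate) | 0.1-0.8 | 0.2-1.4 | 0.5-2.1 |
| ≥ 50% fall | 3-4% | 8-11% | 13-18% |
| Expected in 16 | 0.5-0.6 | 1.3-1.8 | 2.1-2.9 |

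By stratum the two endpoints go opposite ways. Normal, over CV 30-50%: about 1-15% in Stratum I against 0-1.4% in Stratum II. A 50% fall: 2-4% against 4-7% at CV 30%, and 9-16% against 17-29% at CV 50%. At CV 20% the normal rate over all enrolled is only 0.5-2% (medians 1.5, 2 and 3).

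**5. Noise or regression?**

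Mean true level divided by mean observed baseline is 0.94-0.99 at median 1.5, about 1.00 at 2.5 and 1.01-1.05 at 4 (CV 20-50%). Under the assumptions of step 1, scatter around the observed baseline alone gives 1.5-9% normal, against 1.5-11% for the full model. Over all enrolled subjects, regression therefore adds at most about 2 points and can run the other way.

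**6. What averaging does (no drug effect, CV 30/40/50%)**
- ≥ 50% fall, all enrolled: 3-4%, 8-10% and 13-17% on Day 56 alone become 0.4-0.7%, 2-3% and 4-8% on the mean of Days 50, 51 and 56. (The Day 56 rates here come from the same run as the averaged ones and differ from step 4 by up to a point.)
- Normal, baseline < 2 × ULN: 5-11%, 8-16% and 10-21% become 1-4%, 2-7% and 3-10%.
- Requiring a 30% minimum fall leaves the normal rate over all enrolled at 1.5-11%, because the entry floor already forces a fall of at least 23%.

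**The case against.** The best reply is that this is SAP territory. Section 9.6.1.2 yields to the SAP, Section 9.1 promises one, and which collection stands for the end of a period is a usual derivation rule. The protocol does not name Day 56, and since it averages elsewhere, averaging is at least as natural a reading. This stands: the missing definition alone is not an error, and the single-urine figures apply only if the last collection is used. It does not dispose of the ITT default, which the protocol itself states and which leaves one listed endpoint without subjects.

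Second, these are secondary endpoints, and the primary comparison is randomized and placebo-controlled. That also stands and limits the weight of the point. Chance responders in the open-label period do not by themselves favour ATR-101 in the primary analysis.

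A reader might go further in three ways that the documents do not support:
- That the screening rule inflates baseline and so manufactures responders. Step 5 shows this is not general.
- That mild disease will look more responsive. This holds for normalization and reverses for the 50% fall.
- That these proportions are the only efficacy result available for all enrolled subjects. Section 9.6.1.2 also lists change in UFC, late-night salivary cortisol and blood hormones.

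**Conclusion.** The point holds in a limited form. The population problem follows from the protocol's own definitions and needs no assumption: unless the SAP overrides it, the open-label rate is restricted to subjects selected for a low Day 50/51 UFC, and the additional open-label endpoint is empty.

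The noise problem is conditional on using the single Day 56 value and on an assumed CV of 30-50%. It then amounts to about 1-13% normal and 3-18% with a 50% fall when the drug does nothing, or roughly 0 to 3 of 16 subjects on either endpoint. Day-to-day variation is the driver. At CV 20% there is little to correct. The sizes also depend on the assumed case mix, which the protocol does not give. This is worth changing because the remedy is nearly free. It does not undermine the trial's primary result.

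**What to change.** In Section 9.6.1.2:

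1. State that the open-label UFC endpoints (dose escalation and additional open-label period) are evaluated in all enrolled, treated subjects, not ITT.
2. Define the end-of-dose-escalation UFC as the mean of the Day 50, 51 and 56 collections.
3. Add confirmed response, meaning that the criterion is met on both the mean Day 50/51 and Day 56, as a supportive, descriptive result by stratum.

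Items 1 and 2 belong together: averaging within ITT would reuse the very values that selected those subjects. Day 50 is 50 − 29 = 21 days after the last scheduled dose step, but Section 3.1.2 allows down-titration at any time, so the dose actually being taken should be shown with the result. An assumed no-effect rate should not be printed beside the trial's results, since no source in the protocol supports one.

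The cost is wording only, because all three samples are already collected. In simulation (either criterion met, median 2.5 × ULN), sensitivity for a true 60% fall rises from 0.80 to 0.84 at CV 30% and from 0.73 to 0.75 at CV 50%. For a true fall of exactly 50% it drops from 0.59 to 0.58 and from 0.59 to 0.55. The reported open-label response rate may be a little lower. The randomization criteria and the primary endpoint are untouched.
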